11.2. Procedures for Recording and Reporting Adverse Events

11.2.1. Recording Adverse Events

Patients will be instructed to report all AEs and will be asked a general health status question at each study visit. All AEs and SAEs occurring in patients will be recorded in the eCRF from the time of signing the ICF through the Final Study Visit/phone call. An AE will be followed until it is resolved, has returned to baseline, or is determined to be a stable or chronic condition.

At each protocol-required visit (including safety follow-up phone call) during the study, all AEs that have occurred since the previous visit must be reviewed by the Investigator. The Investigator must determine if the AE is serious or nonserious.

The Investigator must assign the following AE attributes:

- AE diagnosis or syndrome(s) if known
 - If not known at time of the report, record the signs and/or symptoms as AEs and provide an updated report with diagnosis when obtained
- Dates of onset and resolution
- Severity as defined per protocol
- Assessment of relatedness to KAN-101/PBO
- Action taken with each KAN-101/PBO dose as a result of the AE

In general, an AE that is the primary cause of subsequent events should be identified by the primary cause (eg, for dehydration due to diarrhea, the AE would be diarrhea). However, AEs occurring secondary to an initiating event that are separated in time should be recorded as independent events (eg, for sepsis secondary to pneumonia, both events should be recorded).

Confirmed and suspected SARS-CoV-2 infections and/or COVID-19 cases will be recorded in the AE eCRF.

11.2.2. Relationship to KAN-101

The Investigator must assess whether the AE may be related to KAN-101 (study drug) or any protocol mandated procedure, when applicable. The relationship is defined below:

Relationship assessments that indicate the event is “Not Drug Related”:

- None: The event is related to an etiology other than the study product administration (the alternative etiology must be documented in the study patient’s medical record).
- Remote: The event is unlikely to be related to the study product and likely to be related to factors other than study product.

Relationship assessments that indicate the event is “Drug Related”:

- Possible: There is an association between the event and the administration of KAN-101, and there is a plausible mechanism for the event to be related to the study

product; but there may also be alternative etiology, such as characteristics of the patient's clinical status or underlying disease.

- Probable: There is an association between the event and the administration of KAN-101, there is a plausible mechanism for the event to be related to KAN-101, and the event could not be reasonably explained by known characteristics of the patient's clinical status or an alternative etiology is not apparent.
- Definite: There is an association between the event and the administration of KAN-101, there is a plausible mechanism for the event to be related to the KAN-101 and causes other than KAN-101 have been ruled out and/or the event re-appeared on re-exposure to KAN-101.

11.2.3. Adverse Event Severity

The Investigator will assess the Grade of the AE per the NCI-CTCAE v5.0 or higher ([Appendix 1](#)). Toxicities that are not specified in the NCI-CTCAE will be defined as follows:

- Grade 1: Mild; asymptomatic or mild symptoms; clinical or diagnostic observations only; intervention not indicated
- Grade 2: Moderate; minimal, local or noninvasive intervention indicated; limiting age-appropriate instrumental activities of daily living (ADL)
- Grade 3: Severe or medically significant but not immediately life-threatening; hospitalization or prolongation of hospitalization indicated; disabling; limiting self-care ADL
- Grade 4: Life-threatening consequences; urgent intervention indicated
- Grade 5: Death related to AE

Note: It is important to distinguish between SAEs and severe AEs. Severity is a measure of intensity, whereas seriousness is classified by the criteria based on the regulatory definitions as described in [Section 11.1.2](#).

11.2.4. Abnormal Laboratory Values

The Investigator is responsible for reviewing clinical laboratory tests determining whether an abnormal value represents a CS change from the patient's baseline value. In general, abnormal laboratory findings without clinical significance (based on the Investigator's judgment) should **not** be recorded as AEs. In general, an abnormal laboratory test result should be reported as an AE if the laboratory result:

- Requires an adjustment or discontinuation of KAN-101
- Requires treatment with or adjustment to concomitant medications
- Is considered to be an AE by the Investigator

11.2.5. Medication Errors, Misuse, and Abuse of KAN-101

Overdose, medication error, misuse, and abuse are defined as follows:

- Overdose: refers to the administration of a quantity of KAN-101 given per administration or cumulative, which is above the maximum dose according to the protocol
- Medication error: refers to an unintentional error in dispensing or administration of KAN-101 not in accordance with the protocol

Off-label use: relates to situations where KAN-101 is intentionally used for medical purpose not in accordance with the protocol

- Misuse: refers to situations where KAN-101 is intentionally and inappropriately not used in accordance with the protocol
- Abuse: corresponds to the persistent or sporadic, intentional excessive use of KAN-101, which is accompanied by harmful physical or psychological effects
- Occupational exposure: refers to the exposure to KAN-101 because of one's professional or non-professional occupation

Overdoses, medication errors, abuse, or misuse will be collected as part of investigational medicinal product dosing information and/or as a protocol violation, as required.

11.2.6. Reporting of Serious Adverse Events

SAEs will be recorded on the appropriate eCRF and reported to the Sponsor within 24 hours of the Investigator's first knowledge of the event, even if the experience does not appear to be related to KAN-101, from the time of signing ICF through the final Follow-Up Visit/phone call.

The initial SAE CRF must be as complete as possible and include details of the current illness and SAE as well as an assessment of the relationship between the event and KAN-101.

Additional information relating to a previously reported SAE must also be reported within 24 hours of the Investigator's first knowledge of information. The Investigator may also be asked, by the Sponsor or designee, to provide clarifications or additional information.

If the Investigator becomes aware of an SAE considered related to KAN-101, occurring more than 30 days after the last dose of KAN-101, the SAE must be reported as described above.

11.2.7. Reporting of Serious Adverse Events to Regulatory Authorities, Ethics Committee, and Institutional Review Board

The Sponsor or designee will determine expectedness of the Sponsor's product for each reported SAE based on the appropriate reference safety information per local country requirements. The Sponsor or designee shall notify regulatory authorities of serious, unexpected, and related AEs or other AEs, per local requirements.

The Sponsor or designee shall notify the Investigator of serious, related, and unexpected AE(s) submitted to the regulatory agencies, per local country requirements.

The Investigator will notify the appropriate Institutional Review Board (IRB)/Local Ethics Committees (LECs) of serious, related, and unexpected AE(s), or significant risks to patients, per

local country requirements. The Investigator must keep copies of all AE information on file, including correspondence with the Sponsor or IRBs/LECs.

11.2.8. Pregnancy and In Utero Drug Exposure

KAN-101 has not been evaluated in pregnant or nursing women. Thus, pregnant women or WCBP who are not using effective contraception are excluded from this study (see [Section 8](#) and [Section 6.1.8](#) for instructions on birth control and pregnancy testing, respectively).

Pregnancies occurring in patients, or partners of male patients are considered immediately reportable events if the pregnancy occurs during the study treatment through the Safety Follow-Up Visit after the patient's last dose of KAN-101. If a pregnancy occurs in a patient, KAN-101 must be discontinued immediately. The pregnant woman should be referred to an obstetrician/gynecologist experienced in reproductive toxicity for further evaluation and counseling.

The pregnancy must be reported to the Sponsor or designee within 24 hours of the Investigator's knowledge of the pregnancy by recording it on the appropriate CRF.

The Investigator will follow the pregnant patient until completion of the pregnancy and must notify the Sponsor of the pregnancy outcome within 24 hours of the Investigator's knowledge of the outcome. The Investigator will provide this information by recording it on the appropriate CRF. This notification includes pregnancies resulting in live, "normal" births.

If the pregnant patient experiences an SAE during pregnancy, or the outcome of the pregnancy meets any of the serious criteria (ie, spontaneous abortion [any congenital anomaly detected in an aborted fetus is to be documented], stillbirth, neonatal death, or congenital anomaly), the Investigator should follow the procedures for reporting SAEs (ie, report the event to the Sponsor or designee within 24 hours of the Investigator's knowledge of the event).

All neonatal deaths and congenital anomalies that occur within 30 days of birth (regardless of causality) should be reported as SAEs to the Sponsor or designee. In addition, any infant death or congenital anomaly occurring after 30 days that the Investigator suspects is related to the in-utero exposure to KAN-101 should also be reported to the Sponsor or designee.

12. STATISTICAL METHODS

Details of the statistical methods for this study will be documented in a Statistical Analysis Plan (SAP). When there is a difference between the final approved SAP and the protocol, the methods described in the final SAP will prevail.

Statistical methods will be primarily descriptive in nature. No hypothesis will be formally tested. For Part A, the data will be listed by dose group. For Part B, summary statistics will be provided by dose group. Categorical variables will be summarized using numbers and percentages. Continuous variables will be summarized by total number (n), mean, standard deviation (StD), median, and range (minimum and maximum).

Part A and Part B PK will be analyzed separately and together where appropriate.

12.1. Sample Size

In Part A, the number of patients enrolled into a cohort will be based on safety and tolerability, and will employ a traditional 3+3 design. Under this model, Part A may enroll between 12 and 24 patients across 4 dose cohorts, depending upon what toxicities are observed. No formal hypothesis testing is planned for Part A. The PK data obtained in Part A will be combined with the PK data obtained following first dose of KAN-101 in Part B.

In Part B, the total sample size of 24 patients (n=18 KAN-101; n=6 PBO) across 3 dose cohorts was chosen to allow for a comparison of safety, PK, and PD between KAN-101 and PBO. A sample size of 6 active patients per cohort in Part B allows for an 0.80 power to detect a treatment-related AE occurring at an event rate of 0.25.

12.2. Analysis Sets

The main analysis sets are defined in this section. Additional analysis sets may be defined in the SAP.

- **The All-Treated Analysis Set** is defined as all patients who received any amount of study drug with treatment group based on the dose level received. This analysis set will be the primary analysis set for all safety endpoints.
- **The PK Analysis Set** will include all enrolled patients who received at least one dose of KAN-101 and have at least one measurement. This analysis set will be used for the analysis of PK parameters as further defined in the protocol.

- CCI [REDACTED]

12.3. Background Characteristics

12.3.1. Patient Disposition

The number and percentage of patients in each disposition category (eg, enrolled, included in each Analysis Set, discontinuing treatment, and discontinuing study, with a breakdown of the reasons for discontinuation) will be summarized by dose level and cohort.

For each part of the study, the All-Treated Analysis Set will be used as the basis for percentages, as appropriate.

12.3.2. Demographics and Baseline Characteristics

The following demographics and baseline characteristics will be summarized by treatment group and cohort for the All-Treated Analysis Set: sex, race, age, years since CeD diagnosis, and years on GFD. Additional parameters may be provided in the SAP.

12.4. KAN-101 Exposure

The summary statistics of exposure will be tabulated by study part and by dose group. In the summary, the following will be included:

- the cumulative number of days of exposure
- the number of IV infusions completed
- the relative dose intensity

All variables are predefined:

- The relative dose intensity is defined as the percentage of the planned treatments completed. It is the ratio of the cumulative actual dose (mg) and cumulative planned dose (mg) times 100. In this definition,
- the cumulative actual dose (mg) is the sum of the actual doses (mg) that the patient receives during the study
- the cumulative planned dose (mg) is the cumulative number of days of exposure times the planned dose level (mg)

All analyses within this section will be based on the All-Treated Set unless otherwise specified.

CCI

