4.3. Dosing Frequency

In Part A, patients will receive a single IV infusion of KAN-101 on D1.

In Part B, patients will receive a total of 3 IV infusions of either KAN-101 or PBO (double-blind). A single IV infusion will be administered on D1, D4, and D7.

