10.2. Dosage and Administration

KAN-101 is provided as a frozen concentrated solution CCI which will be diluted into 250 mL normal saline.

Administration will be by IV infusion over approximately 30 minutes.

For Part A, patients will receive a single IV infusion of KAN-101 only (no PBO).

For Part B, patients will receive 3 IV infusions, each spaced 3 days apart, of a given dose of either KAN-101 or PBO. All doses will be prepared as outlined in the KAN-101-01 Pharmacy Manual by an unblinded pharmacist.

Study treatment (KAN-101 or PBO) should be administered over 30 minutes under the supervision of a physician or other medically qualified study personnel experienced in the use of IV agents and in a facility equipped to manage medical emergencies. In the event of a Grade 3 infusion-related reaction (IRR), the total infusion duration may be increased to 1 hour (please see [Section 10.5](#) for more information). In cases where a temporary interruption is required, the total infusion should be completed within 24 hours of thawing the drug product. See [Section 10.5](#) for detailed guidance regarding infusion administration interruptions due to infusion reactions.

Please refer to the KAN-101 Pharmacy Manual for detailed administration instructions.

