13.8. Study or Clinical Site Termination

The Sponsor, or designee, reserves the right to terminate the study or a clinical study site at any time. Conditions that may warrant termination of the study include, but are not limited to:

- Discovery of an unexpected, serious, or unacceptable risk to patients enrolled in the study
- Decision on the part of the Sponsor to suspend or discontinue testing the study treatment

Conditions that may warrant termination of a study site include, but are not limited to:

- Failure of the Investigator to comply with GCP
- Submission of knowingly false information from the clinical study site to the Sponsor or regulatory authorities
- Insufficient adherence to protocol requirements

If terminating the study, the Sponsor and the Investigator(s) will assure that adequate consideration is given to the protection of the patients' interests.

13.9. Duration of the Study, Expected Duration of Patient Participation, and End of Study

The study is planned to initiate enrollment in January 2020 with the last study visit in June 2021.

In Part A of the study, enrolled patients will receive a single IV infusion of KAN-101 on D1 and will be monitored through D21. Thus, the total length of patient participation, which includes screening, is approximately 49 days.

In Part B of the study, enrolled patients will receive 3 IV infusions of KAN-101, each on D1, D4, and D7, with a final follow-up phone call on D28. Thus the total length of patient participation, which includes screening, is approximately 56 days.

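### Protocol 12.4 words relative dose intensity as the share of planned treatments completed but divides by undefined days of exposure, so in Part B an infusion never given need not lower it

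*Protocol*

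**What the plan says.** Protocol 12.4 plans an exposure summary by study part and dose group with three items: the cumulative days of exposure, "the number of IV infusions completed", and RDI.

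RDI is first defined in words: "The relative dose intensity is defined as the percentage of the planned treatments completed". It is then given as 100 times the ratio of cumulative actual to cumulative planned dose in mg. The numerator is the sum of the mg received. For the denominator, "the cumulative planned dose (mg) is the cumulative number of days of exposure times the planned dose level (mg". The section says its variables are predefined, but days of exposure is defined neither there nor in the readable SAP.

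On population, "All analyses within this section will be based on the All-Treated Set unless otherwise specified". Protocol 12.2 defines that set as "all patients who received any amount of study drug with treatment group based on the dose level received", so a patient who stops early remains in the summary.

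The Part B schedule is intermittent. Protocol 4.3 states "A single IV infusion will be administered on D1, D4, and D7", and Protocol 10.2 states "For Part B, patients will receive 3 IV infusions, each spaced 3 days apart". Protocol 13.9 ends Part B participation "with a final follow-up phone call on D28".

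The readable SAP has no RDI formula and no exposure summary table. SAP 4.8.7 plans a by-subject listing of drug administration and compliance, SAP 4.2 declares no changes from the protocol, and SAP 4.6 refers to a table shells document that is not available here. The opening of Protocol 12 gives the final SAP precedence where the two differ.

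**The concern.** The words count treatments and the formula counts days. With doses on D1, D4 and D7 these are different quantities. Days of exposure is also tabulated as an exposure result in its own right, separately from infusions completed, so the natural reading is a count observed for each patient. A denominator that grows only while the patient is being dosed cannot show doses that were planned but never given.

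If the Protocol 12.4 summary is produced, RDI could stay flat, or rise, while the mean number of infusions in the same table falls. At stake is the interpretation of one descriptive exposure item.

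**Working it through.** The documents state no RDI value, so there is no figure to reproduce. The check applies the formula to the planned schedule.

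**Inputs.** Part B dosing days 1, 4 and 7 (Protocol 4.3); 3-day spacing (Protocol 10.2); end of follow-up D28 (Protocol 13.9); 6 active patients per cohort (SAP 3.2).

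**Formula.** For k full infusions at dose d mg and E days of exposure, RDI = 100 x (k x d)/(E x d) = 100 x k/E. The dose cancels, so the result is the same at every dose level and body weight. The worded definition is 100 x k/3.

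**Stopping between complete infusions, Part B**

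| Reading of E | E for k = 1, 2, 3 | RDI (%) for k = 1, 2, 3 |
|---|---|---|
| Worded definition (planned treatments) | 3, 3, 3 | 33.3, 66.7, 100 |
| First to last dose, inclusive | 1, 4, 7 | 100, 50, 42.9 |
| Dosing days received | 1, 2, 3 | 100, 100, 100 |
| 3-day intervals | 3, 6, 9 | 33.3, 33.3, 33.3 |
| Fixed planned span D1-D7 | 7, 7, 7 | 14.3, 28.6, 42.9 |
| Fixed window D1-D28 | 28, 28, 28 | 3.6, 7.1, 10.7 |
| Planned infusion days | 3, 3, 3 | 33.3, 66.7, 100 |

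In mg, using the SAP 3.5.2 example (0.3 mg/kg x 50 kg = 15 mg), a completer receives 3 x 15 = 45 mg. The formula's planned dose is 7 x 15 = 105 mg on the span, 3 x 15 = 45 mg on dosing days, 9 x 15 = 135 mg on intervals and 28 x 15 = 420 mg on the D28 window.

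**Partly given infusions.** These lower the numerator. Stopping halfway through dose 2 (1.5 doses given):
- span: 1.5/4 = 37.5%, against 42.9% for a completer
- dosing days: 1.5/2 = 75%, against 100%
- intervals: 1.5/6 = 25%, against 33.3%
- wording, counting the half dose pro rata: 1.5/3 = 50%

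Halfway through dose 3 the three readings give 2.5/7 = 35.7%, 2.5/3 = 83.3% and 2.5/9 = 27.8%, again below the completer values. Halfway through dose 1 they give 50%, 50% and 16.7%; here the span value is still above its completer value of 42.9%.

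**Cohort of 6 active, one stopping after a full dose 1.** This can occur: under Protocol 4.9 a Part B patient with a dose-limiting toxicity gets no further doses, and under Protocol 4.7 that patient is not replaced.
- Mean infusions: 16/6 = 2.67, down from 3.00
- RDI as worded: (5 x 100 + 33.3)/6 = 88.9%, down from 100%
- Span: (5 x 42.86 + 100)/6 = 52.4%, up from 42.9%
- Dosing days and intervals: unchanged at 100% and 33.3%
- D1-D28 window: (5 x 10.71 + 3.57)/6 = 9.5%, down from 10.7%

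If the patient is replaced, as SAP 3.2 allows for other reasons, 7 are summarised: infusions 19/7 = 2.71, wording (6 x 100 + 33.3)/7 = 90.5%, span (6 x 42.86 + 100)/7 = 51.0%.

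**Part A.** One full dose gives 1/1 = 100% on the span, dosing-day and planned-infusion readings. A D1-D21 window would give 1/21 = 4.8%. The problem is mainly one for Part B.

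**The case against.** The strongest reply is that this is one undefined term, not an error. The governing sentence and the label cumulative planned dose both point to planned dosing days, which reproduces the wording exactly. A programmer who used the span, the intervals or the D28 window would see completers at 42.9%, 33.3% or 10.7% and stop. The dosing-day reading puts completers at 100%, responds to partial infusions, and sits beside an infusion count that shows the missed doses. The most striking result, RDI rising from 42.9% to 52.4%, comes from the span, which suits intermittent infusions poorly.

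Much of this stands: the size and direction of the effect depend on the reading, and the text names none of them. But planned infusion days is not what the formula says. Days of exposure is itself reported as a result, and each of the three readings in which it accrues with the patient's own dosing departs from the worded value.

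Some stronger inferences are tempting but unsupported:
- *That RDI never falls with early stopping.* It falls on fixed-window readings, and a partial infusion can lower it on all three patient-accruing readings. Such a stop is foreseen in Protocol 10.5, where the remainder of an infusion may not be given.
- *That the SAP dropped the exposure summary without declaring it.* The table shells could contain it, so this cannot be settled from the available documents.
- *That safety conclusions are distorted.* No endpoint, adverse event percentage or escalation rule uses RDI, and early stopping is visible in the infusion count and in the disposition and discontinuation outputs.

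**Conclusion.** The point holds in limited form. As written, the denominator agrees with the worded definition only on a reading the text does not state. For Part B patients stopping between complete infusions, an infusion never given does not lower RDI on the span, dosing-day or 3-day-interval readings: 100/50/42.9%, 100/100/100% and 33.3/33.3/33.3%, against 33.3/66.7/100% in words. Fixed windows move in the right direction but leave a completer at 42.9% (D1-D7) or 10.7% (D1-D28).

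This rests on dosing exactly on D1, D4 and D7 and on complete infusions up to the stop. Priority is low: one descriptive item is affected, mainly in Part B, and the prevailing SAP may not produce it.

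**What to change.** In Protocol 12.4, or in SAP 4.8.7 if RDI is carried there:

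- Define cumulative planned dose as the number of protocol-planned infusions (1 in Part A, 3 in Part B) x planned mg/kg x screening weight, using the mg conversion in SAP 3.5.2. Keep the numerator as written. Part B RDI after 1, 2 or 3 full infusions is then 33.3, 66.7 or 100%, as worded.
- Calculate RDI for KAN-101 patients only. A placebo patient has 0 mg planned and 0 mg received, so the ratio is undefined; report only infusions completed for placebo.
- State that patients are tabulated by dose level received, with any assignment error flagged, because in that case the planned dose in the denominator differs from the reporting group.
- Define days of exposure separately, since it is reported on its own.
- If RDI will not be produced, record that in SAP 4.2 in place of the statement that there are no changes.

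The cost is one formula edit, one definition, a short rule for placebo and assignment errors, and minor programming, or one sentence in SAP 4.2. The denominator needs no new data: screening weight and planned dose level are already recorded.
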